3.1.5 Inclusion of Women and Minorities

Both male and female subjects of all races and ethnic groups are eligible for this study.

3.1.6 Randomization

Randomization will occur after enrollment and must be completed within 45 days of the eligibility screening. If randomization and enrollment are taking place on the same day, then randomization can take place before enrollment. This will allow ample time for the pharmacist to receive the kit assignment.

If eligibility screening procedures were completed on multiple days, patients must be randomized within 45 days of the first day.

Randomization will take place through a third party drug distributor called "Sharp Clinical Services" (Phoenixville, PA). See the "Study Drug Packet" on the ALTE1621 web page on the COG website for details on timing and randomization through the IVRS system.

Sharp Clinical Services will randomize the subject to carvedilol or placebo using a blocked, stratified randomization design with age at diagnosis (2 strata: < 5 years, ≥ 5 years), time since diagnosis (2 strata: < 10 years, ≥ 10 years), and cardiac irradiation (2 strata: any, none), as stratification factors (8 strata total) and a block size of 4 to balance the number of participants in each arm. Blinded study drug will then be assigned to the patient. City of Hope, the coordinating center, will be notified that randomization is complete.

3.2 Patient Eligibility Criteria

Important note: The eligibility criteria listed below are interpreted literally and cannot be waived (per COG policy posted 5/11/01). All clinical and laboratory data required for determining eligibility of a patient enrolled on this trial must be available in the patient's medical/research record which will serve as the source document for verification at the time of audit.

See [Section 7.1](#) for required studies to be obtained prior to starting protocol therapy.

INCLUSION CRITERIA**3.2.1 Current Weight for Males and Females**

3.2.1.1 Males and Females must weigh ≥ 40 Kg.

3.2.2 Age at Cancer Diagnosis

Patient must have had a cancer diagnosis < 22 years of age, irrespective of current age.

3.2.3 Lifetime Anthracycline Dose

Patient must have a lifetime cumulative anthracycline dose of ≥ 250 mg/m² DOXOrubicin equivalent without the protection of dexrazoxane (Zinecard) therapy (see [Section 3.3](#)). The anthracycline dose threshold must be met as part of the treatment of a cancer that was diagnosed at < 22 years of age.

Note: Institutional records (e.g., clinic note, treatment summary, chemotherapy roadmap) can be used to document lifetime receipt of anthracycline dose.

3.2.4 Timing from Cancer Treatment to Study Entry

Patient must have completed cancer treatment ≥ 2 years prior to study enrollment.

EXCLUSION CRITERIA**3.2.5 Cardiac Treatment or Conditions**

3.2.5.1 Receiving treatment for cardiomyopathy or heart failure.

3.2.5.2 Ejection fraction of $< 50\%$ (by radionuclide angiogram or echocardiogram) or shortening fraction of $< 25\%$ (by echocardiogram).

Note: for instances where both are reported, and one is below the threshold, the site will have the option to re-measure it centrally at the core lab.

3.2.5.3 Uncorrected primary obstructive or severe regurgitative valvular disease:

- Nondilated (restrictive); or
- Hypertrophic cardiomyopathy; or
- Significant systemic ventricular outflow obstruction.

3.2.5.4 Sustained or symptomatic ventricular dysrhythmias uncontrolled with drug therapy or implantable device.

3.2.5.5 Significant conduction defects (i.e. second or third degree atrio-ventricular block or sick sinus syndrome).

3.2.5.6 Bradycardia: heart rate < 50 Beats per minute (BPM).

3.2.5.7 Use of an investigational drug or beta adrenergic blockers, including metoprolol, sotalol, within 30 days of enrollment.

3.2.5.8 History of drug sensitivity or allergic reaction to alpha or beta-blockers.

3.2.6 Low Blood Pressure or Blood Pressure Medication

3.2.6.1 Low resting systolic blood pressure: < 90 mmHg.

3.2.6.2 Use of any other blood pressure lowering medication for treatment of hypertension within 30 days of enrollment except calcium channel blockers and diuretics.

3.2.7 Other Exclusion Criteria

- 3.2.7.1 History or current clinical evidence of moderate-to-severe obstructive pulmonary disease or reactive airway diseases (i.e. asthma) requiring therapy.
- 3.2.7.2 Serum AST and/or ALT > 3 times upper limit of institutional normal.
- 3.2.7.3 Gastrointestinal, or biliary disorders that could impair absorption, metabolism, or excretion of orally administered medications.
- 3.2.7.4 Endocrine disorders (such as primary aldosteronism, pheochromocytoma, hyper- or hypothyroidism) not controlled with medication.
- 3.2.7.5 Uncontrolled diabetes (Controlled diabetes per the American Diabetes Association and International Diabetes Center's Glycemic Target Goals is Hemoglobin A1C < 7%).
- 3.2.7.6 Anemia (hematocrit < 28%).
- 3.2.7.7 Currently using select CYP2D6 inhibitor or inducer medications (full list, see [Section 6.1.7](#)).
- 3.2.7.8 Inability to swallow pills.

3.2.8 Pregnancy and Breast Feeding

- 3.2.8.1 Female patients who are pregnant are not eligible. Women of childbearing potential require a negative pregnancy test prior to starting study drug.
- 3.2.8.2 Lactating females are not eligible unless they have agreed to not breastfeed their infants.
- 3.2.8.3 Sexually active female patients of reproductive potential are not eligible unless they agree to use an effective contraceptive method during study and for 2 months after stopping the study drug. Abstinence is an acceptable method of birth control.

3.2.9 Regulatory Requirements

- 3.2.9.1 All patients and/or their parents or legal guardians must sign a written informed consent.
- 3.2.9.2 All institutional, FDA, and NCI requirements for human studies must be met.

3.3 **Cumulative Anthracycline Dose Calculation**

Lifetime cumulative anthracycline dose will be calculated by multiplying the total dose of each anthracycline (doxorubicin, daunorubicin, epirubicin, idarubicin, and mitoxantrone) by a factor that reflects the cardiotoxic potential of each drug and then summing the individual doses.¹²⁴ Conversion factors are shown in Table 2. Any anthracycline dose given with Dexrazoxane will not be counted towards the cumulative dose. Patients who received more than one anthracycline prior to study entry should have each individual agent cumulative dose converted to doxorubicin equivalent and added together (e.g., a patient who received

Agent	Conversion Factor to Doxorubicin Dose
Doxorubicin	Multiply total dose x 1
Daunorubicin	Multiply total dose x 1
Idarubicin	Multiply total dose x 5
Mitoxantrone	Multiply total dose x 4
Epirubicin	Multiply total dose x 0.67

cumulative dose of Daunorubicin at 200 mg/m² and Mitoxantrone 48 mg/m² has a total doxorubicin dose equivalent of 392 mg/m² (200 mg/m² x 1 + 48 mg/m² x 4)).

3.4 Recruitment

Each institution should follow the best recruitment strategy for their site and patients. The below recruitment procedures are recommendations only.

3.4.1 Retrospective Recruitment

Prior participants in any of the active COG long-term cancer survivorship clinics or associated clinical registries who are alive and eligible based on medical record review will be mailed a letter and study brochure describing the study. The letter lets them know that a representative from the study will be calling to tell them more about the study, unless they opt out (i.e., passive refusal). Upon contact, the patient will be given another opportunity to opt out. Patients who agree to be prescreened will be interviewed per the Phone Scripts (see study web page).

3.4.2 Prospective Recruitment

The study will be introduced to eligible patients at the end of their survivorship clinic visit; a brochure describing the study will be given to eligible subjects to take home to read. The study clinical research associate (CRA) or clinical research nurse (CRN) will then follow up with a phone call within approximately 7-10 days to assess interest and confirm interest in eligibility screening. Patients may also self-identify and call in to a local site via recruitment advertising.

3.5 Eligibility Screening

Diagnostic or laboratory studies performed exclusively to determine eligibility for this trial will be done only after obtaining written informed consent. Studies or procedures that were performed for clinical indications (not exclusively to determine eligibility), and no more than 45 days before enrollment, may be used for baseline values even if the studies were done before informed consent was obtained.

3.5.1 Eligibility Screening

Patients will undergo an eligibility screening to assess all the inclusion and exclusion criteria. Patients may be screened and enrolled at the same visit; however, all screening procedures must be completed and reviewed prior to enrollment. All required observations for the eligibility screening are listed in [Section 7.1](#).

4.0 TREATMENT PLAN

Timing of protocol therapy administration, response assessment studies, and surgical interventions are based on schedules derived from the experimental design or on established standards of care. Minor unavoidable departures (up to 72 hours) from protocol directed therapy and/or disease evaluations (and up to 1 week for surgery) for valid clinical, patient and family logistical, or facility, procedure and/or anesthesia scheduling issues are acceptable per COG administrative Policy 5.14 (except where explicitly prohibited within the protocol).

4.1 Overview of Treatment Plan

Subjects will be randomized 1:1 to receive low-dose carvedilol or placebo daily for 24 months. Randomization will be stratified according to rules outlined in [Section 3.1.6](#). Subjects will be instructed to swallow the capsule whole, with water or another non-alcoholic liquid, preferably at the same time each day. They may take the capsules with food. If they forget a dose, participants will be asked to take it when they remember, and then take the next dose as usual, but if they do not remember until their next dose, do not take extra capsules to make up the missed dose.

4.2 Concomitant and Repeat Therapy

No concomitant therapy is allowed with the exception of continued medications for chronic illnesses and necessary medications for unrelated acute illnesses that may occur during the study (cold, flu, infection, etc.). Any such medications must be recorded.

4.3 Dose Escalation and Up-Titration Period

The goal of the up-titration period is to reach the highest dose level that will be continued throughout the maintenance phase. After enrollment and randomization, all subjects will be entered into the up-titration period, during which they will receive carvedilol or placebo. The first dose of the double-blind medication will be administered with food at the clinic. At one- and two- hours after administration of the dose, heart rate and blood pressure will be assessed. The first titration of carvedilol (or matched placebo) will occur two weeks following randomization (± 2 calendar days), with the subsequent titration occurring four weeks later (± 7 calendar days). The initial daily dose will be 3.125 mg once daily. The target final titration dose will be 6.25 mg twice daily (BID) (standard schedule, carvedilol dosing).

The titration dose levels of carvedilol or matched placebo are:

Level	Dose	Frequency
1	3.125 mg	once daily (QD)
2	6.25 mg	once daily (QD)
3	6.25 mg	twice daily (BID)

During the up-titration from level 1 to 2, subjects will be instructed to not take their usual dose of the study medication the morning of their study visit. This dose will be given in clinic, after visit assessments have been completed.

For titration from level 2 to 3, subjects will be instructed to take their daily carvedilol dose the evening prior to their clinic visit, and to refrain from taking the study medication the morning of their study visit. This dose will be given in clinic, after visit assessments have been completed.

At each up-titration visit, the following parameters will be assessed:

- Interim history and physical examination (except Day 0).
- Sitting pre-dose blood pressure and heart rate.
- Sitting 1- and 2-hour post-dose blood pressure and heart rate.
- Concomitant medication assessment.
- Study medication compliance using the Adherence Tracking Form (except Day 0).
- Investigator's assessment of subject's ability to tolerate the study medication, including acute tolerability for at least 2 hours after the first dose of each up-titration level.

If the dose level is judged by the investigator to be tolerated based on the criteria in [Section 4.3.1](#), the dose of carvedilol or matching placebo will be increased to the next level.

4.3.1 Criteria for Assessment of Drug Tolerability Prior to Dose Escalation

The goal of the up-titration period is to reach the highest dose level that will be continued throughout the maintenance phase. Subjects who are unable to tolerate escalation from dose level 1 to 2 (Day 14) will go off protocol therapy. Subjects at dose level 2 will be escalated to dose level 3 or maintained at level 2, depending on tolerability. Dose tolerability will be determined following administration of study drug in clinic. Symptoms will be monitored for a minimum of 2 hours post medication administration. Individuals who meet the following criteria at the end of the evaluation period will be deemed ineligible for dose escalation:

- Low resting systolic blood pressure: < 90 mmHg.
- Bradycardia: heart rate < 50 BPM.
- Sustained or symptomatic ventricular dysrhythmia. Significant conduction defects (i.e. second or third degree atrio-ventricular block) on ECG.
- Dizziness: moderate unsteadiness or sensation of movement (Grade 2 toxicity).
- Flushing: moderate symptoms, limiting instrumental ADL (Grade 2 toxicity).
- Other reasons not listed above, but deemed related to study drug per the investigator.

Prior to escalation to the next dose level, investigators will complete a Dose Escalation Form, confirming that the individual did not demonstrate any of the above signs or symptoms.

4.3.2 Subjects on Dose Level 1 (3.125 mg/Placebo Daily)

At two weeks post-randomization, subjects will return to clinic for a clinical evaluation. During that visit, there will be two options:

- Increase to level 2, *or*
- If dose escalation is considered inadvisable by the investigator, to discontinue the study drug.

Subjects unable to tolerate dose level 1 should be taken off therapy per [Section 8.0](#). Adverse events that occur within 30 days of study drug discontinuation must be reported and followed to resolution. Adverse events considered to be of suspected or probable or definite relationship to study medication will be reported and followed to resolution whenever they occur (see [Section 8.1](#)). The reason for removal from protocol therapy will be recorded.

4.3.3 Subjects on Dose Level 2 (6.25 mg/Placebo Daily)

Four weeks following escalation from dose level 1 to 2, subjects will return to clinic for a clinical evaluation. During that visit, there will be two options:

- Increase to dose level 3, *or*
- Maintain at the current dose level if dose escalation is considered inadvisable by the investigator.

Individuals on dose level 2 who are unable to tolerate dose escalation to level 3 have the option to return in 2 weeks, where there will be another attempt at dose escalation. If at that time, dose escalation is not considered advisable by the investigator, then subjects will remain on dose level 2 for the duration of the study. For these individuals, dose level 2 will be considered the fixed maintenance dose.

4.4 **Maintenance Period**

At the completion of the up-titration period, subjects will enter the maintenance phase of the study which will last 24 months from the first dose of study drug. For the purposes of this study, the initial maintenance visit will be synonymous with the “end of up-titration” visit. Subjects will enter the maintenance phase receiving the highest dose of study medication that was tolerated in the up-titration phase. This may be dose level 2 or 3.

During the maintenance period, study visits will be scheduled on 90, 180, 365, 540, and 730 days. These study visits may occur within +/- 10 business days of the calculated visit day. Additional visits may be scheduled by the investigator, as appropriate, based on clinical indication. The study CRA/CRN will follow-up with a telephone call in between clinic visits, as outlined below.

4.5 **Follow-up Visits**

Study participants will be asked to return their pill kits on Day 90 for a pill count, refill of the medication, and clinical evaluation; patient reported symptoms will be accessed via a standardized Symptom Log (see study web page on the COG website). For the Day 90 visit only, the patient has the option to do an in-person visit or a phone follow up, depending on their ability to easily return to the clinic.

Subsequent return clinic visits will occur on Days 180, 365, 540 and 730 following randomization. The following parameters will be assessed according to the study observations (see [Section 7.1](#)).

On Days 270, 455, and 630 a phone visit will be conducted (these calls may occur within \pm 10 business days of the calculated due date). During the telephone call, there will be collection of patient reported symptoms via standardized Symptom Log, medication refill, and pill count reported on the Adherence Tracking Form.

A City of Hope Adverse Event (AE) collection form will be submitted by study personnel on Days 180, 365, 540, and 730.

4.6 **Long-term Follow-up**

After trial completion, study participants will continue clinic follow-up per standard of care, with their first return visit scheduled one year after their Day 730 study visit. All organ function assessments included in the COG survivorship guidelines

(www-survivorshipguidelines.org) should be performed, including an echocardiogram. Special attention should be paid to symptoms and signs of cardiac dysfunction on all subsequent annual follow-up survivorship clinic visits. Follow up should be reported using the long-term cardiac outcomes report form for 3 years after the Day 730 study visit.

Monitoring for cardiac dysfunction that may occur after the two-year intervention, will occur during the annual survivorship clinic visits which will include a complete physical examination and an echocardiogram per the COG survivorship guidelines. Information regarding new cardiac events will be obtained from the survivorship clinic using the Cardiac and Other Event Form.

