8.0 CRITERIA FOR REMOVAL FROM PROTOCOL THERAPY AND OFF STUDY CRITERIA

8.1 Criteria for Removal from Protocol Therapy

- a) Physician determines it is in the patient's best interest.
- b) Inability to tolerate dose escalation from level 1 to level 2.
- c) Treatment interruption longer than 90 consecutive days.
- d) A cardiac event (see [Section 8.1.1](#) for definition).
- e) Pregnancy.
- f) Adverse Event requiring removal from protocol therapy (see [Section 13.4](#)).
- g) Diagnosis of a new malignancy requiring systemic chemotherapy or radiation.
- h) Adherence < 50% in any 90 day period.
- i) Emergency un-blinding (see [Section 5.0](#))
- j) Study is terminated by Sponsor.

Patients who are taken off protocol therapy do not require any additional study observations/evaluations unless they experienced a cardiac event or have become pregnant.

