9.2 Patient Accrual and Expected Duration of the Trial

It is estimated that approximately 50-60% of the 450,000 survivors of childhood cancer who are alive in the U.S. today have received anthracyclines. Many pediatric cancer patients (approximately 20-25%) are being treated with anthracyclines with cumulative dose ≥ 250 mg/m², such as those with bone cancer and AML. Although exact estimates are not available, using the conservative estimates of 50% and 20% to calculate, $>30,000$ survivors would meet the current eligibility criteria. We expect thousands of childhood cancer survivors meeting such criteria are currently being followed at member COG institutions.

ACTIVATION PROTOCOL:

To answer the scientific questions, 250 randomized subjects (125 per arm) is required. Through a different mechanism, 82 patients have already been accrued and randomized. Therefore, this COG protocol aims to enroll and randomize an additional of 168 patients through this protocol, with a maximum accrual of 177 patients to account for up to 5% of ineligible enrollments. Given the large pool of potential eligible patients, we expect to complete the accrual, including the time it takes to open the study at COG institutions, over 4 years.

WITH AMENDMENT #4:

To answer the scientific questions, 182 subjects (91 per arm) who are randomized and start study drug are required. Through a different mechanism, 87 patients have already been accrued and randomized. Therefore, this COG protocol aims to enroll, randomize and start

treatment for an additional **95** patients through this protocol. To account for attrition, enrollment through this COG trial may proceed up to 109 patients. Given the large pool of potential eligible patients, we expect to complete the accrual, including the time it takes to open the study at COG institutions, over 5 years.

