Age at exposure to anthracyclines – continuous, time-invariant. We will also categorize per the stratification factor for randomization.

Latency from radiation therapy – continuous, time-varying. We will examine if intervention effects vary by time since exposure to therapeutic radiation.

C. Molecular characteristics

The following variables are known to influence efficacy of carvedilol in the treatment of HF patients and will be analyzed at a later date.

CYP variants – dichotomous (yes/no), constant over the study period

$\beta_{1, 2}$ and α_1 -Adrenergic receptor and Norepinephrine transporter variants ([Section 2.5](#)) – dichotomous (yes/no), constant over the study period.

In addition to testing their significance as effect modifiers, we will also examine their relationship with the outcome variables (LV T-D, ESWS, Natriuretic peptides, MPI etc.) to validate known relationships. Proc Mixed for normal data and Proc GLMMIX for non-normal data in SAS 9.1 (Cary, North Carolina) will be used for analysis.

9.3.5 Exploratory Aim 1.3:

To evaluate the long-term efficacy of carvedilol in preventing cardiomyopathy and/or heart failure in high-risk childhood cancer survivors.

For this exploratory aim, long term overall and cardiac health status will be described for study participants and as exploratory analyses compared between the 2 study arms.. The majority of these childhood cancer survivors are expected to be in active follow-up and routine clinical information (including annual echocardiograms) is already being collected as part of the patients' standard care. In support of this aim, ascertainment of basic information regarding overall and cardiac health status: vital status, development of cardiomyopathy/heart failure, most recent ejection fraction and shortening fraction data in order to determine if there has been a cardiac event (as defined in [Section 8.1.1](#)) for up to 5 years after study enrollment.

9.4 **Power and Sample Size**

Primary Aim - Determine the impact of a two-year course of carvedilol on LV T-D:

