The longitudinal power calculations were conducted using the program RMASS2.¹²⁹ We assumed a Type I error of 0.05, power of 0.80, 2-sided test, linear trend, and compound symmetry correlation matrix ($[\rho]$ ranging from 0.6 to 0.9). An attrition rate of 19% per arm/year (voluntary withdrawal, discontinuation due to drug intolerance, unexpected events [pregnancy/ relapse]) was assumed. Table 4 shows the minimum effect size at 24 months that can be detected for a given correlation between measures. For example, with 91 individuals in each group, we have 80% power to detect a difference of at least 0.38 in LV T-D z-score between the two arms if the correlation between baseline and the 2 year LV T-D z-score is 0.6. With regards to the secondary endpoints of efficacy, 3-6 mL increases in LVESV, 6-10 mL increases in LVEDV, or 3-5% drops in LV EF (from normal resting LV EF) have been associated with adverse cardiovascular outcomes in clinical trials with patients with preserved or mildly depressed EF.¹³⁰⁻¹³² Thus, effect sizes presented in Table 4 are plausible and clinically meaningful.

Secondary Aim – Establish safety and tolerability of the two-year course of carvedilol.

ACTIVATION PROTOCOL:

Adverse events: We assume the rate of Grade 2-4 toxicities in the placebo group to be low, at 5%. At the end of the study, assuming 88 individuals remaining in each arm (15% attrition/year from the original 125/ arm), the study will have at least 80% power to detect

an adverse event rate of 19.2% in the carvedilol group based on Fisher's exact test and Type I error=0.05.

Adherence to therapy: We will examine the difference in adherence rates by comparing the percent adherence by treatment group. With 125 study participants at baseline per arm, assuming a constant adherence rate of 90% in the placebo group, a between-measurement correlation of 0.6, 15% yearly attrition, and 2-sided alternative, there will be 80% power to detect an adherence rate of 75% in the carvedilol group.

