Voluntary withdrawals: We assume that the proportion of patients in the placebo arm who will withdraw voluntarily by 24 months is 20% (10%/year); of note, this is less than the assumed overall attrition rate of 15%/year because attrition could occur due to other reasons such as toxicities, cancer recurrence, etc. With 125 patients in each arm at baseline, using Type I error=0.05, the study will have 80% power to detect a >15% absolute difference in the voluntary withdrawal rates between the two study arms.

WITH AMENDMENT #4:

Adverse events: We assume the rate of Grade 2-4 toxicities in the placebo group to be low, at 5%. At the end of the study, assuming 56 individuals remaining in each arm (19% attrition/year from the 91/arm at baseline), the study will have at least 80% power to detect an adverse event rate of 24.7% in the carvedilol group based on Fisher's exact test and Type I error=0.05.

Adherence to therapy: We will examine the difference in adherence rates by comparing the percent adherence by treatment group. With 91 study participants at baseline per arm, assuming a constant adherence rate of 90% in the placebo group, a between-measurement correlation of 0.6, 19% yearly attrition, and 2-sided alternative, there will be 80% power to detect an adherence rate of $\leq 70\%$ in the carvedilol group.

Voluntary withdrawals: We assume that the proportion of patients in the placebo arm who will withdraw voluntarily by 24 months is 26% (13%/year); of note, this is less than the assumed overall attrition rate of 19%/year because attrition could occur due to other reasons such as toxicities, cancer recurrence, etc. With 91 patients in each arm at baseline, using Type I error=0.05, the study will have 80% power to detect a >21% absolute difference in the voluntary withdrawal rates between the two study arms.

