9.5.2 Plans for Interim Monitoring for Superiority and Futility

ACTIVATION PROTOCOL:

The statistician will perform up to two blinded interim analyses for efficacy and futility after 33% and 66% of patients have completed all the study endpoints. Patients that were taken off study due to an adverse event or cardiac event after

Day 180 would also be included in the interim analyses. The DSMC will stop the trial for clear evidence of superiority or futility if the test statistic on blinded data falls within the specified early stopping boundary ([Appendix II](#), Tables s1 and s2). In both the interim and final analysis, the intent-to-treat data set will be the primary analysis group, with consideration of missing data.

WITH AMENDMENT #4:

With the amended total n=182, 114 patients are anticipated to complete all study time points, after accounting for attrition. As of 6/30/2020, 87 patients had data at all time points, corresponding to 76% of the anticipated revised sample size of n=114. Since this is close to the final expected updated sample size, no interim analysis for efficacy will be performed, but one futility analysis will be performed using the data available at 6/30/2020 ([Appendix II, Table s3](#)).

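### Long-term reporting for Aim 1.3 runs from the Day 730 visit, so none is required for most patients who stop early, although Section 9.3.5 promises ascertainment to 5 years from enrollment and an arm comparison

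*Combined protocol and SAP*

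**What the plan says.** Aim 1.3 (Section 1.3) concerns the long-term prevention of cardiomyopathy and heart failure. For this aim, Section 9.3.5 says that "long term overall and cardiac health status will be described for study participants and as exploratory analyses compared between the 2 study arms". It lists vital status, cardiomyopathy or heart failure, and the latest ejection and shortening fractions, to be ascertained "for up to 5 years after study enrollment". It relies on information that routine survivorship care already produces.

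Section 4.6 sets the collection schedule. The first long-term visit falls one year after Day 730, and "Follow up should be reported using the long-term cardiac outcomes report form for 3 years after the Day 730 study visit". A second paragraph covers dysfunction arising after the two-year intervention and says that new cardiac events will come from the survivorship clinic on an event form.

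The last sentence of Section 8.1 says that patients taken off protocol therapy "do not require any additional study observations/evaluations unless they experienced a cardiac event or have become pregnant". Section 8.2 lists four off-study criteria: (a) withdrawal of consent for data submission, (b) death, (c) completion of planned assessments and (d) loss to follow-up. Stopping study drug is not one of them.

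The sizes come from the Amendment #4 text. Section 9.2: "182 subjects (91 per arm) who are randomized and start study drug are required". Section 9.4: "An attrition rate of 19% per arm/year (voluntary withdrawal, discontinuation due to drug intolerance, unexpected events [pregnancy/ relapse]) was assumed". The adverse-event calculation in 9.4 works from "assuming 56 individuals remaining in each arm (19% attrition/year from the 91/arm at baseline". Section 9.5.2: "114 patients are anticipated to complete all study time points, after accounting for attrition".

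**The concern.** A patient who stops drug early remains on study under 8.2 and is still a participant under 9.3.5. That patient has no Day 730 visit to start the clock in 4.6, and 8.1 tells the site that nothing more is needed. The exception makes this worse for an outcome analysis. A patient removed because of a cardiac event is covered by it. A patient removed for intolerance who develops heart failure a year later is not.

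Stopping can plausibly depend on treatment. Removal reasons in 8.1 include failure to escalate from level 1 to level 2, adverse events and low adherence. Section 6.1.2 lists fatigue and dizziness in more than 20% of patients on carvedilol. Section 9.3.1 itself allows that dropout may differ between the arms, and answers with pattern-mixture and selection models for the primary endpoint. Section 9.3.5 has no counterpart for Aim 1.3.

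At stake is the only aim directed at cardiomyopathy and heart failure themselves rather than surrogates. If 4.6 and 8.1 are followed as written, its comparison covers completers plus early stoppers selected by what happened to them after randomisation.

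**Working it through.** **1. The two clocks**

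- *Completer.* 2 years on study plus 3 years of the form = 5 years. Sections 4.6 and 9.3.5 agree.
- *Early stopper without a cardiac event or pregnancy.* 4.6 gives no start date, 8.1 requires nothing, 8.2 keeps the patient on study, and 9.3.5 still expects data to 5 years. The sections conflict.
- *Early stopper with a cardiac event or pregnancy.* The 8.1 waiver does not apply. 4.6 still gives no start date.

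**2. Reproducing the plan's attrition figure**

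Inputs: 91 per arm and 182 in total (9.2); 19% per arm per year for 2 years (9.4).

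- Linear, n × (1 − 2 × 0.19): 91 × 0.62 = 56.4, against the stated 56. In total, 182 × 0.62 = 112.8, against the stated 114 (about 1% apart).
- Compound, n × 0.81²: 91 × 0.656 = 59.7 and 182 × 0.656 = 119.4. Neither matches.

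The plan therefore uses linear attrition. Patients not reaching Day 730: 91 − 56 = 35 per arm, and 35/91 = 38.5%. From the total, (182 − 114)/182 = 68/182 = 37.4%. Both are close to 2 × 19% = 38%.

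**3. How many of the 35 could be followed under a better rule**

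The 38% includes voluntary withdrawals, which 9.4 puts at 26% by 24 months in the placebo arm. Some of these patients may also withdraw consent for data. The plan does not say how many, so I take the two extremes, applying 26% to either arm:

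- None withdraws consent for data: all 91 can be followed, a gain of about 35 per arm.
- All withdraw consent for data: 91 × (1 − 0.26) = 67.3 can be followed, a gain of 67.3 − 56.4 = 10.9, or about 11 per arm.

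The 11 is approximate. The remaining 12 points of attrition (38% − 26%) include pregnancies, which 8.1 already exempts, and may include some patients lost to follow-up.

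**4. Follow-up time at the upper bound**

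With linear attrition to 62% at 2 years and nothing collected after stopping:

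- Years 0–2: (1 + 0.62)/2 × 2 = 1.62 years per patient.
- Years 2–5: 0.62 × 3 = 1.86 of 3 years, so 38% is missing.
- Total: 1.62 + 1.86 = 3.48 of 5 years, so about 30% is missing.

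**The case against.** The strongest reply is that no section excludes early stoppers. Section 9.3.5 speaks of study participants and counts from enrollment. Section 4.6 has a second route through the survivorship clinic and the event form. The 8.1 waiver may be meant only for the Section 7.1 calendar, which ends at Day 730. Section 14.0 refers to a form submission schedule on the group's website that is not in these documents and could cover early stoppers.

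Part of this stands: the defect is an unreconciled conflict and a missing rule, not a declared exclusion. It does not remove the point. Routine care produces data in the clinic but does not tell a site to submit a form, or when. The event-form paragraph is also framed as following the two-year intervention and gives no schedule for a patient who left it early. The only reporting period stated is tied to Day 730.

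Three stronger readings are tempting, and the documents do not support them:

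- *Early stoppers have no follow-up.* The text supports only that none is required of most of them under 4.6 and 8.1.
- *The arms are not compared as randomised.* Section 9.3.5 names no analysis set. A selected comparison is the consequence of following 4.6 and 8.1 literally, not something the plan states.
- *An inert drug would appear to cut events by about 21%.* This takes 26% v 47% withdrawal, using the 21-point detectable gap in 9.4, with an equal constant hazard. Follow-up is then 1.74 + 0.74 × 3 = 3.96 years on placebo and 1.53 + 0.53 × 3 = 3.12 years on carvedilol, a ratio of 0.79. It is hypothetical and applies only to events per randomised patient, a measure the plan never specifies. Events per person-year would give a ratio of 1.0. The gap is a detectable difference, not an expected one, and Section 2.3.3 cites placebo-controlled paediatric carvedilol studies with equivalent withdrawal rates.

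**Conclusion.** The point holds as a conflict between Sections 4.6 and 8.1 on one side and 9.3.5 on the other. As written, required long-term reporting depends on reaching Day 730 or, after an early stop, partly on already having had the outcome. The Aim 1.3 comparison would then rest on a post-randomisation selection.

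Up to 35 of 91 per arm (38%) are affected on the plan's own linear attrition. This is an upper bound on what the rule costs; between about 11 and 35 per arm could be recovered, on the stated assumption about consent. The direction of any bias cannot be given from the documents, since it depends on who stops in each arm and why.

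The aim is exploratory, with no power statement or decision rule, and the primary LV T-D analysis is unaffected. The change is still worth making: it is cheap, and outcomes not collected from early stoppers may be hard to recover later.

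**What to change.** - **Section 4.6:** count the long-term cardiac outcomes form from enrollment. Require it yearly to 5 years for every randomised patient, including those off protocol therapy, unless the patient is off study under 8.2(a), (b) or (d).
- **Section 8.1, last sentence:** exempt this form from the waiver.
- **Section 9.3.5:** state that all randomised patients are compared by assigned arm, with an analysis that accounts for unequal follow-up, for example time to first event censored at the last report. Censoring deals with unequal time but not with informative loss, so also report by arm how many patients have long-term data.

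The cost is amendment wording and one form a year for roughly 11 to 35 more patients per arm, filled in from survivorship visits and echocardiograms that the protocol already treats as routine care. Some early stoppers will be hard to reach. No treatment or clinical rule changes.
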